Diagnosis and Main Inclusion Criteria	
Patients must fulfill the following criteria to be eligible for the study:
 
1. Male or female patient \geq 18 years of age.2. Evidence of a personally signed and dated informed consent document indicating that the patient (or a legal representative) has been informed of all pertinent aspects of the study.3. Patients who are willing and able to comply with scheduled visits, treatment plan, laboratory tests, and other study procedures

	
4. Newly Patient with Philadelphia chromosome positive chronic phase CML and BCR-ABL1 transcript detected at diagnosis.5. ECOG Performance Status of 0, 1, or 2.6. Adequate hepatic, renal and pancreatic function defined as:
a. Total bilirubin within normal range or Direct bilirubin $\leq 1.5 \times$ ULN,b. Aspartate aminotransferase (AST)/Alanine aminotransferase (ALT) $\leq 2.5 \times$ upper limit of normal (ULN) or $\leq 5 \times$ ULN if attributable to liver involvement of leukemia,7. Women of childbearing potential must have a negative pregnancy test documented prior enrollment. Women of childbearing potential and men must be using an adequate method of contraception.

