
Number of Patients	36 patients of both genders
Approximate Duration of Patient Participation	Approximately two years with treatment (25 cycles of 28 days).
Approximate Duration of Study	The estimated duration of the clinical trial is approximately 36 months, including 12 months for enrollment and 26 cycles of treatment/follow-up.
Approximate Number of Study Centers	Up to 10 centers; national (Spain).
Dosage Administration	
Group 1: The first 10 patients:
 
1. One cycle only with bosutinib 400 mg/day therapy.2. 2 cycles with bosutinib 400 mg/day plus atezolizumab 840 mg q2w therapy.3. 10 cycles with bosutinib 400 mg/day plus atezolizumab 1680 mg q4w therapy.4. 12 cycles with bosutinib 400 mg/day therapy. 
Group 2: The next 26 patients:
 
1. One cycle only with bosutinib 400 mg/day therapy.2. 12 cycles with bosutinib 400 mg/day plus atezolizumab 1680 mg q4w therapy.3. 12 cycles with bosutinib 400 mg/day therapy.
Efficacy Evaluation	Hematologic response rate, cytogenetic response rate, molecular response rate, and disease progression will be assessed according to standard criteria, as follows: 
• Bone marrow aspirates for assessment of cytogenetic response every 3 months after initiating bosutinib treatment. After complete cytogenetic response (CCyR) has been achieved, only if there is suspicion of disease progression,• BCR-ABL assessment to determine molecular response every 3 months after initiating bosutinib treatment,• Complete blood count (CBC) for assessment of hematologic response every 3 months,• Survival follow-up.
Safety Evaluation	Safety assessments will include physical and laboratory examinations. AEs will be graded according to the NCI CTCAE, v5.0. All patients receiving at least 1 dose of bosutinib will be considered evaluable for safety. The AE and VOE incidence rates, as well as the frequency of occurrence of overall toxicity -categorized by toxicity grades (severity). Listings of laboratory test results will also be generated, and descriptive statistics summarizing the changes clinically significant in laboratory tests over time will be presented.

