10.2 Inclusion Criteria

Patients eligible for inclusion in this study have fulfill the following criteria:

1. Male or female patient \geq 18 years of age.
2. Evidence of a personally signed and dated informed consent document indicating that the patient (or a legal representative) has been informed of all pertinent aspects of the study.
3. Patients who are willing and able to comply with scheduled visits, treatment plan, laboratory tests, and other study procedures
4. Newly Patient with Philadelphia chromosome positive chronic phase CML and BCR-ABL1 transcript detected at diagnosis.
5. ECOG Performance Status of 0, 1, or 2.
6. Adequate hepatic, renal and pancreatic function defined as:
 - a. Total bilirubin within normal range or Direct bilirubin \leq 1.5 x ULN,
 - b. Aspartate aminotransferase (AST)/Alanine aminotransferase (ALT) \leq 2.5 x upper limit of normal (ULN) or \leq 5 x ULN if attributable to liver involvement of leukemia,
7. Have a negative pregnancy test documented prior to enrollment (for females of childbearing potential). A woman is considered of childbearing potential, i.e. fertile, following menarche and until becoming post-menopausal unless permanently sterile. Permanent sterilisation methods include hysterectomy, bilateral salpingectomy and bilateral oophorectomy (CTFG, 21/09/2020). These women, must have a negative serum or urine pregnancy test before initiation of study treatment and must also use highly effective methods of contraception while enrolled in the study. The use of highly effective contraception should continue for at least 14 days after the last dose of study treatment. Acceptable forms of highly effective contraception methods include (CTFG, 21/09/2020):
 - a. Total abstinence [when this is in line with the preferred and usual lifestyle of the patient. Periodic abstinence (e.g., calendar, ovulation, symptothermal, post-ovulation methods) and withdrawal are not acceptable methods of contraception]
 - b. Male/female sterilization. These defined as:
 - Female sterilization (have had surgical bilateral oophorectomy with or without hysterectomy) or tubal ligation at least six weeks before taking study treatment.
In case of oophorectomy alone, only when the reproductive status of the woman has been confirmed and documented by follow-up hormone level assessment.

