12.3 Eligibility Screening

The investigator will send the eligibility check form to the Sponsor by email ([contact]). The investigator will be allowed to assign treatment to the patient if he/she fulfills all inclusion criteria and none exclusion criteria.

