13.14 Contraception and Pregnancy

Females of childbearing potential and fertile males will be informed of the potential risk of conception while participating in this study. Females of childbearing potential are required to use a highly effective form of contraception from recruitment through at least 4 months after the end of treatment (see inclusion criterion 7)

A pregnancy test will be performed on each premenopausal female of childbearing potential within 7 days prior to first dose of bosutinib, and again each month during the study, at the end-of-treatment visit and at the end-of-study visit. A negative pregnancy test must be documented prior to administration of study drug.

Females should be advised to take a pregnancy test if their period is late, and to inform their investigator of the result.

If a patient is confirmed pregnant during the trial, study drug administration must be discontinued immediately. The investigator must also immediately notify the sponsor medical monitor of this event and record the pregnancy on a pregnancy form. Initial information regarding a pregnancy must be immediately (in less than 24 hours) forwarded to FTH Pharmacovigilance and Risk Management or its designated representative.

The investigator must immediately report follow-up information to the sponsor regarding the course of the pregnancy, including perinatal and neonatal outcomes, regardless of whether the patient has discontinued participation in the study. If the pregnancy results in the birth of a child, additional follow-up information may be requested. If the pregnancy results in spontaneous abortion or stillbirth, that event should be reported as a SAE.

Pregnancy outcomes must also be collected for the female partners of any males who took study drug in this trial. Consent to report information regarding these pregnancy outcomes should be obtained from the female partner.

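### Synopsis criterion 7 requires contraception of men at entry, but Protocol 10.2, SAP 5.2 and Protocol 13.14 state that duty for women only; 10.2 and 13.14 also give women different post-treatment periods

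*Protocol*

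**What the plan says.** In Protocol section 5 (Synopsis), item 7 of the main inclusion criteria is one of the conditions a patient has to meet to be eligible. It reads: "Women of childbearing potential and men must be using an adequate method of contraception".

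The full criterion 7 in Protocol 10.2 is addressed to females of childbearing potential and states their contraception duty: "These women, must have a negative serum or urine pregnancy test before initiation of study treatment and must also use highly effective methods". It then sets how long this lasts: "The use of highly effective contraception should continue for at least 14 days after the last dose of study treatment". Men appear only in the list of accepted methods, where male sterilisation is an option and is explained through the vasectomised partner of a female patient. SAP 5.2 repeats this criterion almost word for word.

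Protocol 13.14 says: "Females of childbearing potential are required to use a highly effective form of contraception from recruitment through at least 4 months". That period is counted from when treatment ends, and the section refers back to inclusion criterion 7. For men it says two things: "Females of childbearing potential and fertile males will be informed of the potential risk of conception while participating in this study", and "Pregnancy outcomes must also be collected for the female partners of any males who took study drug in this trial".

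Protocol 12.3 governs entry: "The investigator will be allowed to assign treatment to the patient if he/she fulfills all inclusion criteria and none exclusion criteria". The synopsis gives the planned enrolment as "36 patients of both genders".

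**The concern.** Two statements of the same numbered criterion do not cover the same people. A synopsis normally shortens the body of a protocol. Here it adds a duty, on men, that the body does not contain. Section 12.3 ties treatment assignment to meeting the inclusion criteria without saying which statement of them counts. Section 18.3 asks monitors to verify adherence to the criteria in full, and section 17.9 has significant deviations reported in the study report. Two sites, or a site and its monitor, could therefore classify the same man differently: eligible under 10.2, ineligible under the synopsis.

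The second mismatch concerns women. Section 13.14 cites criterion 7 as its reference, yet criterion 7 gives a much shorter minimum. A site reading only 10.2 could tell a woman that her obligation ends after 14 days, when 13.14 keeps it in force for months longer.

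What is at stake is consistent eligibility decisions and consistent pregnancy precautions in a trial whose primary objective is safety. No dose-limiting toxicity rule, response rate or sample size depends on it.

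**Working it through.** The main point is a comparison of texts, so no plan figure needs to be reproduced.

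**Step 1. Who carries the duty?**

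| Text | Women of childbearing potential | Men |
|---|---|---|
| Protocol 5, Synopsis, criterion 7 | Contraception required (adequate method) | Contraception required (adequate method) |
| Protocol 10.2, criterion 7 | Contraception required (highly effective method) | No duty stated; male sterilisation listed as a method |
| SAP 5.2, criterion 7 | As 10.2 | As 10.2 |
| Protocol 13.14 | Contraception required (highly effective form) | Informed of risk; partner pregnancy outcomes collected; no duty stated |

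Of the three protocol places, one states a duty for men. The SAP text is a copy of 10.2 and does not govern enrolment, so it is not separate evidence of what was intended.

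**Step 2. Does the difference change a decision?** Take a man who is not using contraception and meets every other criterion. Under 10.2 he is eligible, because nothing there requires contraception of him. Under the synopsis he is not. Now take a man who is using an adequate method. He is eligible under both. The texts therefore disagree about one kind of patient only, and the stricter reading always satisfies both.

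**Step 3. How many men?** The only input is that the 36 patients are of both sexes. The documents give no planned sex split, and nothing on fertility, partner status or contraceptive use. No estimate is possible.

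**Step 4. The separate duration point, women only.** Inputs: a minimum of 14 days after the last dose (10.2), and a minimum of 4 months after the end of treatment (13.14).

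- With 28-day months: 4 × 28 = 112 days, and 112 − 14 = 98 days' difference. The 28-day month is the convention of Protocol 12.1, where it is stated for visit timing; using it here is an assumption.
- With calendar months of 30.44 days (assumed): 4 × 30.44 ≈ 122 days, and 122 − 14 = 108 days' difference.

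Both periods are minimums. Observing 4 months after the end of treatment also meets the 14-day minimum, so the longer period satisfies both texts.

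**The case against.** The strongest reply is that nothing is contradictory. Neither 10.2 nor 13.14 says that men may go without contraception; they leave out a requirement that the synopsis states. The synopsis is part of the protocol and binds sites, and a site that follows it complies everywhere. Section 12.3 also has the eligibility check form sent to the sponsor, which is a chance to catch a discrepancy. That form and the consent text were not available to us, and either may address men. The remark in 10.2 that limits the vasectomy condition to female patients could suggest that male sterilisation was also meant for male patients.

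Much of this stands. It makes the problem an incomplete carry-over between sections rather than two rules that cannot both be obeyed. It does not remove the problem: listing a method creates no duty, and a site that uses the detailed criteria in 10.2 as its checklist has no prompt to ask a man about contraception.

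A reader might also infer that the 14-day and 4-month periods prevent a rule for men from being written into 10.2. The documents do not support that. The synopsis sentence is an entry condition with no end date and could be copied as it stands. The 98 to 108 days describe the women's provisions and measure nothing about men.

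**Conclusion.** The concern holds as a minor eligibility and safety consistency correction. One protocol place of three states a contraception duty for men, and a site working from 10.2 could enrol a man whom the synopsis excludes. Separately, the women's minimum post-treatment periods differ by roughly 98 to 108 days, depending on how a month is counted.

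The size of the first point cannot be given in patients. A reader might infer that ineligible men have been or will be enrolled, that partners are exposed to a demonstrated risk, or that the sponsor meant men to be exempt. The documents show none of these: they contain no enrolment data by sex, no data on risk to partners, and no statement of which text reflects the intention. The conclusion rests on the current wording of the protocol and SAP alone and could be softened by the eligibility check form or the consent text. No analysis figure changes.

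**What to change.** 1. **Men.** Carry the synopsis sentence, "Women of childbearing potential and men must be using an adequate method of contraception", into criterion 7 of Protocol 10.2, and align 13.14 and the copy in SAP 5.2. The highly effective standard that 10.2 already sets for women should stay in place beside it. If the sponsor confirms that men are not meant to be bound, delete the reference to men from the synopsis instead. Accepted methods for men, and any post-treatment period for them, are for the sponsor to set, because no document text states either.

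2. **Women.** In criterion 7 of 10.2 and in SAP 5.2, replace the 14 days with the 4 months after the end of treatment in 13.14. This satisfies both texts and makes the cross-reference in 13.14 correct.

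**Cost.** A written amendment under Protocol 17.10, approved by sponsor and investigators, and also by the health authorities and ethics committee if judged substantial. It can travel with the next amendment. It changes a few sentences, adds no visit, test or sample, and needs no re-analysis. The eligibility check form in 12.3 should be checked against the agreed wording at the same time.

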6 BACKGROUND

6.1 Chronic Myeloid Leukemia: Pathogenesis and Treatment

Chronic Myeloid Leukemia (CML) is a hematological stem cell disorder associated with a specific chromosomal translocation known as the Philadelphia (Ph) chromosome; it is found in 95% of patients (Nowell and Hungerford 1960; Rowley 1973). The translocation consists in the fusion of the ABL proto-oncogene with the BCR gene, resulting in the production of an activated form of the ABL protein-tyrosine kinase (Bartram *et al*, 1983; Heisterkamp *et al*, 1983). Expression of the BCR-ABL protein causes leukemia in mice, suggesting this protein is linked to disease pathogenesis (Daley *et al*, 1990; Kelliher *et al*, 1990).

Clinically, CML progresses through three distinct phases of increasing refractoriness to therapy: chronic phase (CP) (median duration 3-4 years; median survival up to 10 years with allogenic bone marrow transplant and 5-6 years with interferon (IFN)), accelerated phase (AP) (median duration 3-9 months; median survival 8-18 months), and blast crisis (BC) (median survival 3-6 months) (Enright & McGlave 2000). Most patients suffer the CP form, which is characterized by splenomegaly and leukocytosis with generally few symptoms.

National Comprehensive Cancer Network (NCCN) guideline on CML (NCCN guideline v1.2019) (Radich, 2018) and European Leukemia Net (ELN) (Steegmann *et al*, 2016) recommend continuing tyrosine kinase inhibitor (TKI) treatment (i.e., imatinib, nilotinib, dasatinib, ponatinib, bosutinib) indefinitely in all responding patients. Treatment discontinuation may be considered in individual patients, also outside studies, if proper, high-quality, and certified monitoring can be ensured at monthly intervals.

Imatinib (IM) rapidly became the gold standard therapy in CML that dramatically changed the prognosis of the disease (Druker *et al.*, 2006). More potent second-generation tyrosine-kinase inhibitors (TKI) have been consecutively developed to counteract resistance to IM in a substantial proportion of patients such as dasatinib, nilotinib, bosutinib and ponatinib. Efficacy of second and third generation TKIs was first shown in second-line therapy for patients intolerant or resistant to IM. Superiority of dasatinib and nilotinib over IM was thereafter demonstrated in first-line therapy (DASISION and ENESTnd phase III trials), in terms of achievement of complete cytogenetic response (CCyR) at 12 months and an increased rates of major molecular responses (MMR) and deep molecular responses (Fujisawa S *et al.*, 2014; Larson RA *et al.*, 2012).

6.2 Overview of Bosutinib

Bosutinib is an oral, once-daily, second-generation tyrosine kinase inhibitor, with a manageable and distinct safety profile. Bosutinib exhibits dose-proportional increases in exposure between 200 and 600 mg, and its absorption increases with food. It has extensive tissue distribution, is highly bound to plasma proteins, and is primarily metabolized in the liver by cytochrome P450 (CYP) 3A4. Hepatic and renal impairment increases the exposure to

bosutinib. Metabolic drug–drug interactions of bosutinib are limited in scope to CYP3A inhibitors and inducers but are significant in their extent. Coadministration of bosutinib with strong or moderate CYP3A inhibitors or inducers should be avoided (Abbas, 2016).

Bosutinib is used for the treatment of chronic phase (CP), accelerated phase (AP), and blast phase (BP) Philadelphia chromosome-positive chronic myelogenous leukaemia (Ph+ CML) previously treated with one or more tyrosine kinase inhibitor(s) [TKI(s)] and for whom imatinib, nilotinib and dasatinib are not considered appropriate treatment options (EMA, 2019).

This indication for bosutinib is based principally on the results of an open-label, single-arm, multicenter, phase 1/phase 2 study in adults with chronic, accelerated, or blast phase CML following therapy with either imatinib alone or imatinib followed by dasatinib and/or nilotinib; patients were intolerant of or had a disease that was resistant to imatinib. In this study, 546 patients received bosutinib 500 mg once daily (increased to 600 mg daily if complete hematologic or cytogenetic response was not achieved by week 8 or 12, respectively). The median duration of therapy with bosutinib was 22 months in patients with chronic phase CML previously treated with only imatinib; patients previously treated with imatinib followed by dasatinib and/or nilotinib received therapy with bosutinib for a median duration of 8 months (EMA, 2019; FDA, 2019).

At the time of data analysis, patients with chronic phase CML previously treated with imatinib alone or imatinib followed by dasatinib and/or nilotinib had been followed for at least 23 or 13 months, respectively. The primary efficacy end point of this study was major cytogenetic response (defined as elimination or substantial reduction [by at least 65%] of Ph+ hematopoietic cells) at 24 weeks. In this study, resistance to imatinib was defined as failure to achieve or maintain any hematologic improvement within 4 weeks of therapy; or failure to achieve a complete hematologic response by 3 months, a cytogenetic response by 6 months, or a major cytogenetic response by 12 months; or disease progression after a previous cytogenetic or hematologic response; or evidence of the genetic mutation in the Bcr-Abl gene associated with imatinib resistance. Imatinib intolerance was defined as inability to tolerate imatinib because of toxicity, or disease progression with imatinib and inability to receive a higher dosage because of toxicity. Definitions of resistance and intolerance to both dasatinib and nilotinib were similar to those for imatinib. Major cytogenetic response was achieved at 24 weeks in 34% of patients in chronic phase CML who were previously treated with imatinib alone and in 27% of those previously treated with imatinib followed by dasatinib or nilotinib. At the time of data analysis, median durations of response had not been reached. Disease progression (i.e., transformation from chronic phase to accelerated or blast phase CML) occurred in 4.3% of patients with chronic phase CML. In an exploratory analysis, treatment with bosutinib resulted in confirmed complete hematologic responses at 48 weeks in 30 or 15% of patients in accelerated or blast phase CML, respectively; the median duration of therapy with bosutinib for these patients previously treated with at least imatinib who were in

the accelerated or blast phase of the disease was 10 or 3 months, respectively (EMA, 2019; FDA, 2019).

More recently, bosutinib was also authorized in adult patients with newly-diagnosed chronic phase (CP) Philadelphia chromosome-positive chronic myelogenous leukaemia (Ph+ CML) (EMA, 2019) based on the results obtained in the BEFORE study (Cortes, 2018a). In this study bosutinib was compared with imatinib in 536 newly diagnosed CML patients in the 'chronic phase'. The main measure of effectiveness was the number of patients who had a 'major molecular response'. After one year of treatment, 47% (116 out of 246) of patients treated with bosutinib had a major molecular response, compared with 37% (89 out of 241) of patients treated with imatinib.

Diarrhea is the most frequent side effect related to bosutinib in clinical trials (80% any grade, <10% of grade 3–4). This side-effect is usually well-managed with dose reductions/interruptions, since <1% of the patients treated with bosutinib in the BEFORE study discontinued treatment due to diarrhea (Cortes, 2012; Cortes, 2018b). In general, pleural effusion is a rare complication in bosutinib treated patients. However, patients who had pleural effusion while on dasatinib and later received bosutinib treatment had a high risk of recurrence of this complication (Gambacorti, 2018). Cardiac and vascular toxicity have been evaluated in bosutinib treated patients enrolled in clinical trials showing a good safety profile. Similar incidences were observed with bosutinib (first or later lines) or comparing to imatinib treated patients (Cortes, 2016). A decrease in the glomerular filtration rate has been observed with long-term exposure to bosutinib. Renal AEs were reported in 73/570 patients (13%) receiving bosutinib as a second-line or later treatment, and in 22/248 (9%) receiving bosutinib as first-line treatment (Cortes, 2017).

6.3 **Overview of Atezolizumab**

Atezolizumab is a monoclonal antibody targeting programmed death ligand 1 (PD-L1 or CD274 antigen). PD-L1 is thought to play an important role in suppressing the immune system triggered by disease, by reducing the proliferation of antigenspecific CD8+ T-cells and controlling the accumulation of foreign antigen-specific T-cells. Up-regulation of PD-L1 has been suggested as a mechanism used by cancer cells to evade the host immune system (Markham, 2016). Atezolizumab has been approved in Europe (EMA, 2019) as monotherapy for the treatment of adult patients with locally advanced or metastatic urothelial carcinoma (UC):

- after prior platinum containing chemotherapy, or
- who are considered cisplatin ineligible, and whose tumours have a PD-L1 expression ≥ 5%.

Also, in combination with bevacizumab, paclitaxel and carboplatin, atezolizumab is indicated for the first-line treatment of adult patients with metastatic non-squamous non small cell lung cancer (NSCLC). In patients with EGFR mutant or ALK-positive NSCLC, atezolizumab, in

combination with bevacizumab, paclitaxel and carboplatin, is indicated only after failure of appropriate targeted therapies.

Atezolizumab as monotherapy is indicated for the treatment of adult patients with locally advanced or metastatic NSCLC after prior chemotherapy. Patients with EGFR mutant or ALK positive NSCLC should also have received targeted therapy before receiving atezolizumab.

Atezolizumab at a dose of 1–20 mg/kg produced a dose-proportional increase in exposure to the drug. Typical clearance was 0.20 L/day, volume of distribution at steady state was 6.9 L, and the terminal half-life was 27 days, according to a population analysis of patients in the dose range (n = 472). This population analysis also suggested steady state occurs after 6–9 weeks treatment (2–3 dosage cycles). Systemic accumulation in terms of area under the plasma concentration time curve (AUC), maximum concentration (C_{max}) and trough concentration (C_{min}) was 1.91, 1.46 and 2.75-fold, respectively. The systemic exposure to atezolizumab was not significantly affected when analysed according to patient age, body-weight, gender, positive anti-therapeutic antibody status, albumin levels, tumour burden, region or race, mild or moderate renal impairment, mild hepatic impairment, level of PD-L1 expression, or Eastern Cooperative Oncology Group (ECOG) performance status. The potential for atezolizumab to interact with other drugs is unknown (*Markham, 2016; EMA, 2019*).

Major common AEs involved fatigue, decreased appetite, nausea, diarrhea, pyrexia, pruritus, cough, edema peripheral, and rash. The most common severe AEs were fatigue, anemia, and dyspnea. The overall atezolizumab-related death rate was much lower than chemotherapeutics-related death rate. Atezolizumab has better overall survival and lower risk of AEs compared with chemotherapy (*Tie, 2019*).

